7.2 PATIENT REGISTRATION

Eligibility will be checked before registration confirmed by the Sponsor. The patient will be a screening failure if not all inclusion criteria are met, if any exclusion criterion is met, or if the Sponsor does not approve registration. Regardless of circumstances, Investigators will not be allowed to treat any patient before appropriate receipt of the Sponsor's agreement to proceed with registration. A patient should only be treated if eligibility criteria are still met according to assessments performed closest to first drug administration.

A patient who has been treated without the Sponsor's agreement may not be considered evaluable for the primary endpoint of the study and may need to be replaced (although can continue in treatment provided this does not pose a risk to the patient until discontinuation for any other reason).

For patients included in the study (all registered patients) but never treated, only baseline and off-study visit modules of the e-CRF should be completed but serious adverse events (SAEs) occurring during screening need to be reported (using paper SAE forms).

For screen failures (patients who started screening but were not finally registered), only the screening form of the e-CRF should be completed but SAEs occurring during screening need to be reported (using paper SAE forms).

7.3 RANDOMIZATION

Not applicable.

7.4 EVALUATIONS DURING TREATMENT

The assessments to be done while the patient is on treatment are shown in [Table 9](#).

Table 9. Evaluations during treatment.

	ASSESSMENT	TIME
1. Clinical examination	Physical examination: Including weight and clinical assessment. BSA and dosing should be recalculated in the event of weight variation of $\pm 10\%$ from baseline. ECOG performance status (Appendix 1).	Day 1 of Cycle 2 and subsequent cycles (always prior to drug administration). Also repeat on Day 1 of Cycle 1 (prior to drug administration) if more than 10 days have passed since the screening assessment.
	Vital signs: HR, ABP, and temperature.	Day 1 of Cycle 2 and subsequent cycles (always prior to drug administration). Also repeat on Day 1 of Cycle 1 (prior to drug administration) if more than 10 days have passed since the screening assessment.
2. Laboratory tests	Hematology: Complete blood count, differential WBC (neutrophils, lymphocytes), hemoglobin, and platelets. Biochemistry-A: ALP, AST, ALT, total bilirubin (and direct bilirubin if total is $>1.5 \times$ ULN), GGT, creatinine/CrCL (Cockcroft-Gault formula, Appendix 2), glucose, LDH, and serum electrolytes (Na^+ , K^+ , Total calcium).	Day 1 of Cycle 2 and subsequent cycles (always prior to drug administration). Also repeat on Day 1 of Cycle 1 (prior to drug administration) if more than 10 days have passed since the screening assessment. If any clinically-relevant, treatment-related grade ≥ 3 AE occurs, the abnormality should be reassessed at least every 2–3 days until recovery to at least grade 2. In the event of febrile neutropenia, grade 4 neutropenia and/or grade 4 thrombocytopenia, reassessment should be performed daily until recovery to at least grade 3 (or until fever resolution, if applicable) and then every 2–3 days thereafter until recovery to at least grade 2
	Biochemistry-B: Total proteins and albumin.	Day 1 of Cycle 2 and subsequent cycles (always prior to drug administration). Also repeat on Day 1 of Cycle 1 (prior to drug administration) if more than 10 days have passed since the screening assessment.
3. Pregnancy test	Assessment of β -hCG only if the patient is a WOCBP (Appendix 3).	Repeat every cycle or (at least) every month while on-treatment.
4. Cardiac assessment	ECG: Including rhythm definition and PR interval; heart rate; QT interval (raw); QRS complex duration, as well as any ECG anomaly or variation (change in grade) with respect to baseline.	Repeat if clinically indicated.
	LVEF: ECHO or MUGA scan	
5. Pharmacokinetics	Ten plasma PK samples are required from patients included in the first stage of the study: just before start of administration, just before EOI, and then 15 min, 30 min, 1 h, 2 h, 4 h, 6 h, and 12.5 h (Day 1) and 24.5 h (Day 2) after EOI. Only eight plasma PK samples are required from patients included in the second stage of the study: the samples scheduled at 12.5 h and 24.5 h after EOI are not required.	Days 1 and 2 of Cycle 1 and Cycle 2 in all patients included in the first stage. Day 1 of Cycle 1 and Cycle 2 in all patients included in the second stage. See Table 10 .
6. Metabolomics	Three blood samples should be collected	One prior to each dose administration on Day 1 and Day 8 of Cycle 1, and also on Day 8 of Cycle 2.

	ASSESSMENT	TIME
7. Pharmacogenomics	For those patients who consent to participate in the substudy, archived paraffin-embedded tumor tissue samples should be available.	The availability of tumor tissue samples used for the initial diagnosis of the disease, or obtained at relapse, should be confirmed and should be prepared and shipped during the trial following the instructions detailed in a separate laboratory manual.
8. Pharmacogenetics	If the patient consents to the substudy, an additional blood sample for PGt analysis should be collected.	At any time during the trial but ideally at the same time as the pretreatment PK sample (sample #1) in Cycle 1.
9. Disease assessments	
Clinical/radiological tumor assessment: Using RECIST v.1.1. Helical i.v. and oral contrast-enhanced CT-scan (if appropriate) for chest, abdomen and pelvis and other areas of suspected diseases. If i.v. contrast is contraindicated for the CT-scan, chest evaluation should be performed using non-contrasted CT and abdomen/pelvis evaluation using gadolinium-enhanced MRI.
 
The same radiological method should be used throughout the study for each individual patient. Anonymized copies of images showing a response (CR or PR) must be submitted to the Sponsor. Tumor markers alone or chest radiography alone are not sufficient to assess tumor burden.
	To be performed every six weeks (+ 7 days, except for Week 12 when a window of \pm 5 days applies).
10. Concomitant medications	All concomitant therapies taken by the patient (including any not prescribed by the Investigator) should be documented with indication.	Throughout the on-treatment period.
11. Adverse events	Grading should be as per the NCI-CTCAE v.4.	Throughout the on-treatment period.
	PRO QLQs: Patients will be asked to complete the EORTC QLQ-CIPN20 and QLQ-C30.	On Day 8 (day of second dose administration) of every treatment cycle.

Registration=confirmation of eligibility and inclusion; A patient should only be treated if eligibility criteria are still met according to assessments performed closest to first drug administration. Day 1=day of first cycle administration (with infusion start); Day 8=seven days after the first dose administration of a cycle (\pm 2 days); Day 22 = Day 1 (\pm 2 days) of the following cycle.

Permitted windows for assessments before Day 1 of Cycle 1:

If physical examination, ECOG PS, vital signs, hematology/biochemistry were assessed >10 days before Day 1 of Cycle 1, the tests must be repeated within 2 days before the first study drug administration.

If pregnancy test was done >7 days before Day 1 of Cycle 1, the test must be repeated within 2 days before the first study drug administration.

If tumor assessments were done >28 days before Day 1 of Cycle 1, the tests must be repeated within 2 days before the first study drug administration.

A patient should only be treated if eligibility criteria are still met according to assessments performed closest to treatment start.

Permitted windows for assessments after Day 1 of Cycle 1:

- 2 days for clinical assessments (physical examination, ECOG PS, vital signs), always before study drug administration.

+ 7 days for tumor assessments (except in week 12 when there is a maximum 5-day window).

\pm 2 days for Day 1 study drug administration (from Cycle 2 onwards).

\pm 2 days for Day 8 study drug administration.

- 2 days for laboratory tests. To confirm criteria for treatment continuation, laboratory assessments must be performed within 2 days prior to drug administration.

If a drug administration is delayed beyond the permitted protocol window, assessments planned for the original administration day must be repeated on the day the dose is finally administered.

ABP, arterial blood pressure; AE, adverse event; ALP, alkaline phosphatase; ALT, alanine aminotransferase; AST, aspartate aminotransferase; β -hCG, beta subunit of human chorionic gonadotropin; BSA, body surface area; CrCL, calculated creatinine clearance; CR, complete response; CT, computed tomography; ECG, electrocardiogram; ECHO, echocardiogram; ECOG, Eastern Cooperative Oncology Group; EOI, end of infusion; EORTC, European Organisation for Research and Treatment of Cancer; EOT, end of treatment; GGT, gamma-glutamyltransferase; HR, heart rate; IC, Informed Consent; i.v., intravenous; LDH, lactate dehydrogenase; LVEF, left ventricular ejection fraction; MRI, magnetic resonance imaging; MUGA, multiple-gated acquisition; NCI-CTCAE, National Cancer Institute Common Terminology Criteria for Adverse Events; PGt, pharmacogenetics; PK, pharmacokinetics; PR,

	ASSESSMENT	TIME
--	------------	------

partial response; PRO, patient reported outcomes; PS, performance status; QLQ, quality of life questionnaire; RECIST, Response Evaluation Criteria in Solid Tumors; SAE, serious adverse event; ULN, upper limit of normal; WBC, white blood cells; WOCBP, woman of childbearing potential.

7.5 EVALUATIONS AT END OF TREATMENT

The EOT visit should take place approximately 30 days (\pm 15 days) of the last study drug administration, unless the patient starts any subsequent antitumor therapy, in which case the EOT visit should be performed immediately before the start of the new therapy (ideally the day before or the same day). If a patient dies within 30 days from the last dose, the date of death will be considered EOT.

The assessments listed below are required if no recent data are available (i.e. within the previous 10 days) or if the last data available show a grade \geq 2 treatment-related alteration, whenever the medical condition of the patient allows.

- Assessment of disease-related symptoms.
- Complete physical examination (including weight).
- ECOG PS.
- Vital signs (heart rate, blood pressure, body temperature).
- Concomitant therapies.
- Hematology.
- Biochemistry-A.
- Biochemistry-B.
- Pregnancy test (if patient is a WOCBP).
- LVEF.
- PRO QLQs (EORTC QLQ-CIPN20 and QLQ-C30)
- Adverse events.

For individual patients (and if clinically indicated according to Investigator's criteria), it might also include the following:

- ECG.
- Other tests as appropriate.

Adverse events must be reported during 30 days after the last study drug administration. All SAEs occurring within 30 days of the last study drug administration will be reported. Beyond this period of time, only those suspected to be treatment-related SAEs will be reported (Section [8.5.2](#)).

The Sponsor will evaluate all safety information that is spontaneously reported by an Investigator beyond the time frame specified in the protocol.

Loss to follow-up, or failure to attend the EOT visit due to a deteriorated clinical condition or due to personal reasons such as returning to their previous hospital, will not be considered protocol deviations.

7.6 FOLLOW-UP AFTER THE END OF TREATMENT VISIT

After EOT, patients will be followed every four weeks until resolution or stabilization of toxicities (if any). During follow-up, the QLQ-CIPN20 should be completed every

three months until the start of a new antitumor therapy; unless the patient discontinued treatment due to grade ≥ 3 PN, in which case, repeat the assessment monthly until recovery to grade ≤ 2 (or until start of subsequent antitumor therapy).

The primary endpoint of the study is PFS3, defined as the percentage of patients remaining alive and progression-free at Week 12. Therefore, the Week-12 disease evaluation should be performed in all non-PD patients. Tumor assessment should be performed about every three months during follow-up in patients who discontinue treatment without disease progression.

Regardless of the reason for treatment discontinuation, all patients will be followed about every three months until death, refusal to continue participating in the study, or study termination (clinical cutoff), whichever occurs first. Subsequent antitumor therapies should be provided until death, refusal, and/or clinical cutoff (whichever occurs first).

Patients without disease progression who discontinue treatment due to a drug-related AE must be followed both for the AE and for efficacy.

Progression-free Survival and Survival Follow-up Timelines for the Whole Population:

If the study ends after the futility analysis at 24 evaluable patients (first stage):

- Patients who are still on study will be followed up to 12 weeks after the first PM060184 administration of the last patient evaluable for the futility analysis.

If the futility analysis results in continuation of recruitment (second stage):

- All patients will be followed up to 12 months after the first PM060184 administration of the last evaluable patient treated in the study, regardless of the stage at which the patients have been included.

For the purpose of collecting information on patient's survival, a documented telephone call, email or medical chart review is acceptable; follow-up for survival will be completed for all patients only if the study continues to the second stage.

7.7 STUDY TERMINATION (CLINICAL CUTOFF)

The planned study termination date (clinical cutoff) will be: 12 months after the first PM060184 administration of the last evaluable patient treated in the study.

7.8 PHARMACOKINETICS

The plasma PK of PM060184 will be evaluated in Cycle 1 and Cycle 2 during both stages of the study. In the first stage, PK will be evaluated on Days 1 and 2 of Cycle 1 and Cycle 2 with a sampling schedule of ten samples; in the second stage, PK will be evaluated on Day 1 of Cycle 1 and Cycle 2 only with eight samples ([Table 10](#)). Concentration data will be pooled with that from other clinical studies with PM060184 as a single agent and PK parameters will be calculated by means of population PK analysis and/or non-compartmental methods.

Table 10. Pharmacokinetic sampling schedule for PM060184.

Sample number	Day	Relative times	Sampling times for PM060184	Sampling window
#1	1	0 min	Before start of administration	-
#2	1	30 min	Just before EOI	- 2 min
#3	1	45 min	15 min after EOI	± 2 min
#4	1	1 h	30 min after EOI	± 5 min
#5	1	1.5 h	1 h after EOI	± 10 min
#6	1	2.5 h	2 h after EOI	± 10 min
#7	1	4.5 h	4 h after EOI	± 10 min
#8	1	6.5 h	6 h after EOI	± 10 min
#9 ^a	1 ^a	12.5 h	12 h after EOI	± 1 h
#10 ^a	2 ^a	24.5 h	24 h after EOI	± 4 h

^a Samples #9 and #10 are required only in patients included in the first stage of the study. EOI, end of infusion; h, hour; min, minute.

The accurate recording of actual sampling times is more important than strict adherence to the scheduled times.

Blood samples for PK analysis will be obtained through a peripheral vein located in the contralateral side to that of drug administration, whenever possible. In any case, the sampling vein has to be different to that in which drugs are administered. Even the last sample **must never be collected from the catheter used for drug administration**.

A separate manual describes in more detail the required procedures. Please read it carefully before PK sampling. In short, after collection, each sample will be centrifuged and the resulting plasma layer transferred into a new tube for the determination of PM060184 concentration. The plasma-containing tubes will be stored frozen until their shipment to the Central Laboratory for further delivery to the Laboratory for PK Samples (see Study Contacts). All the material for PK procedures will be provided by the Central Laboratory.

Once all samples from a patient have been collected, they should be shipped for analysis to the Central Laboratory as soon as possible, ideally on the next shipping day. If the same site has samples from several patients, the samples can be sent in the same shipment. However, **the time span between the collection time of the last PK sample from a patient and the shipment of all the samples from that patient to the Central Laboratory should not exceed one week**.

7.9 METABOLOMICS

Metabolomics (the determination of endogenous low-molecular-weight molecules or metabolites in a body fluid and their changes as a consequence of stimuli such as medical interventions), is currently being used to evaluate the efficacy and safety of medical interventions in cancer ([11](#)), thus allowing for the discovery of predictive biomarkers of drug response ([12](#)).

The metabolomics of PM060184 will be characterized by evaluating systemic variations in pre- and post-treatment metabolic profile to identify potential biomarkers of PK, safety and/or efficacy response to PM060184.

Three blood samples are required for this analysis. Patients will have one blood sample collected before each drug administration on Day 1 and Day 8 of Cycle 1, and also on Day 8 of Cycle 2, to evaluate the pretreatment profile of endogenous metabolite levels and changes after PM060184 treatment.

Blood must be collected without anticoagulant and with a separating gel, allowed to clot, and centrifuged. Serum will be collected and stored. The samples should be frozen at -80°C within 24 h. If not possible, they can be frozen at -20°C , but only for a maximum period of two weeks before shipping in dry ice to the central laboratory.

The required procedures for the collection, processing and storage of the sample for metabolomics are described in more detail in the laboratory manual. Please read it carefully before sample extraction.

7.10 PHARMACOGENETICS

To explore PGt factors that may help to explain individual variability in main PK parameters, as well as susceptibility to develop treatment-related AEs, the presence or absence of germline mutations or polymorphisms that may be involved in the metabolism and/or transport of PM060184 will be analyzed in leukocyte DNA extracted from blood collected at any time during the trial but ideally at the same time as the pretreatment PK sample (sample #1) in Cycle 1 from those patients who have also consented to the substudy.

The collection and management of this additional sample are quite different from those for PK assessment. Please carefully follow the instructions detailed in a separate manual. The assessment of polymorphisms is not affected by treatment; hence, the Sponsor may require the collection of additional samples later on, if the first assessment has not been performed accurately.

Only patients who voluntarily sign the IC for the PGx/PGt substudy will participate in the PGt evaluation. Refusal to participate in the PGx/PGt substudy will not affect patient participation in the clinical study PM60184-B-002-17.

7.11 PHARMACOGENOMICS

Provision of samples for PGx analyses will be optional and performed upon patient consent by signing the substudy ICF. For those patients who consent to participate in the substudy, the availability of tumor tissue samples used for the initial diagnosis of the disease, or obtained at relapse, should be confirmed and should be prepared and shipped during the trial following the instructions detailed in a separate laboratory manual.

The objective of the PGx substudy is to evaluate the role of potential markers of sensitivity to treatment with microtubule-interacting agents in a population of advanced CRC patients treated with PM060184. These molecular markers would help in the future selection of patients who might preferentially benefit from PM060184 therapy, thus contributing to improved health care through a more individualized medicine.

Analyses will be performed at the Central Laboratory for PGx samples (see Study Contacts). The analytical methods required for this molecular characterization analysis

are described in a separate document detailing the procedures to be followed for sample collection, labeling, and shipment.

The following analyses will be performed on paraffin-embedded tumor tissue samples from patients participating in the substudy if there is evidence of clinical benefit:

- Quantification of protein and/or mRNA expression levels of tubulin isotypes and other factors related to the mechanism of action of PM060184 and to the tumor microenvironment by immunohistochemistry (IHC) or quantitative polymerase chain reaction (PCR) in tumor tissue microarrays constructed from the patients' samples.
- Analysis of polymorphisms and mutations of the above-mentioned selected genes, if relevant, by reverse transcription polymerase chain reaction (RT-PCR) and/or DNA sequencing.
- Analysis of BRAF-mutant-like gene expression subtypes (and potentially full genome expression).

If possible, expression levels of the different markers will be correlated with the study efficacy parameters.

8. STUDY EVALUATIONS

8.1 EFFICACY

Patients will be evaluable for efficacy if they receive at least one complete treatment cycle (or two PM060184 dose administrations over two cycles) and have, at least, one disease assessment at Week 6 and another one at Week 12.

In addition, any patient who presents disease progression, symptomatic deterioration due to the disease or clinical progression, dies due to malignant disease, discontinues treatment due to unmanageable toxicity, or dies or discontinues treatment due to a treatment-related AE before evaluation of the response at Week 12 will also be considered evaluable for the primary endpoint and classified as a non-responder.

Patients who have no disease assessment at Week 6 but remain on treatment and are assessed at Week 12 (or later, and with no evidence of disease progression) will be considered evaluable for efficacy.

Patients who refuse further treatment before Week 12 due to reasons other than related AEs not considered unmanageable toxicity will be replaced.

A futility analysis will be performed once the first 24 evaluable patients complete the Week 12 (\pm 5 days) tumor assessment; progress; die due to PD; or discontinue treatment due to unmanageable toxicity (whichever occurs first). If seven patients or more achieve PFS3, then 36 additional patients will be recruited (second stage).

Tumor assessment will be measured using RECIST v.1.1 ([17](#)).

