6.2 DURATION OF THE STUDY (PER PATIENT)

Patients will be evaluated at scheduled visits in the following study periods:

- **Screening:** from signature of informed consent to registration (confirmation of eligibility) or screen failure.
- **Pretreatment:** from registration to first dose of study treatment.
- **Treatment:** from the first administration of the study treatment to end of treatment (EOT). EOT is standardly defined as 30 days (\pm 15 days) after the day of last administration of study treatment, unless the patient starts a new antitumor therapy or dies within 30 days of the last dose, in which case the date of administration of this new antitumor therapy or the date of death will be considered the EOT date.
- **Follow-up:** after EOT, patients will be followed for both safety and efficacy.
 - 1) **Safety:** every four weeks until resolution or stabilization of drug-related AEs (if any).
 - 2) **Efficacy:** about every three months until death, refusal to continue participating in the study, or study termination (clinical cutoff), whichever occurs first.

Subsequent off-study antitumor therapies should be provided until death, refusal and/or clinical cutoff (whichever occurs first).

Note: patients without disease progression who discontinue treatment due to a drug-related AE must be followed both for the AE and for efficacy.

Patients will be considered to be **on-study** from the signature of the informed consent form (ICF) to the end of the follow-up period (or screening failure). Investigators can appraise potential study candidates in a pre-screening period but only perform study-specific screening assessments after the patient formally consents. Patients will be considered to be **on-treatment** from the date of first dose until EOT.

Patients may withdraw their consent at any time; if consent to study participation is withdrawn, no further study activities will be conducted on them (Section [6.3.3](#)). If consent only to receive the study treatment is withdrawn, treatment will be stopped and other study procedures performed as normal (see [7.5](#) and [7.6](#) below).

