9.3 SAMPLE SIZE

Patients will be treated with PM060184 to test the null hypothesis (H0) that 30% or less patients are alive and free of progression at twelve weeks (PFS3) according to RECIST v.1.1 ($p \leq 0.30$) versus the alternative hypothesis (H1) that 50% or more patients are alive and free of progression at 12 weeks according to the aforementioned criteria ($p \geq 0.50$). The variance of the standardized test is based on the null hypothesis. The type I error (alpha) associated with this one-sided test is 0.025 and the type II error (beta) is 0.1; hence, statistical power is 90%.

Sixty evaluable patients are necessary to test the hypothesis. A futility analysis using O'Brien-Fleming boundaries is planned when 24 patients can be evaluated (first stage). If there are seven or more patients achieving PFS3 in the first stage then the trial will proceed to a second stage and a total of 60 patients will be recruited.

If at least 25 of 60 evaluable patients are alive and free of progression at 12 weeks then the null hypothesis can be rejected and PM060184 considered active and deserving potential development in this setting.

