Patients must be replaced if they are considered not evaluable for efficacy for the primary endpoint (PFS3), i.e., if they are withdrawn from the study due to significant clinical deterioration of unknown reason, hypersensitivity reactions, unrelated AEs without any tumor assessments after the start of study treatment, if they refuse further treatment before Week 12 due to reasons other than related AEs not considered unmanageable toxicity, if they receive less than one complete treatment cycle (at least two PM060184 dose administrations over two cycles unless treatment discontinuation was due to unmanageable toxicity), or do not have the disease assessment at Week 12 (except in the cases outlined above).

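### Patients who refuse further treatment before Week 12 are replaced even when their Week-12 status is known, in conflict with other evaluability rules, so the denominators for 7/24 and 25/60 are not fixed

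*Protocol*

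**What the plan says.** **The replacement rule.** Protocol 8.1, fourth paragraph, reads: "Patients who refuse further treatment before Week 12 due to reasons other than related AEs not considered unmanageable toxicity will be replaced". The synopsis (efficacy evaluations) and the definition of the efficacy-evaluable set in SAP 4 carry the same sentence. The replacement paragraph of SAP 4 lists, among the reasons a patient is not evaluable for PFS3, "if they refuse further treatment before Week 12 due to reasons other than related AEs not considered unmanageable toxicity". A missing Week-12 assessment is a separate item in that list, so refusal works as a ground of its own. SAP 4.2 bases the primary analysis on the efficacy-evaluable set.

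**The Week-12 evaluation.** Protocol 6.2: "If consent only to receive the study treatment is withdrawn, treatment will be stopped and other study procedures performed as normal". Protocol 7.6: "Therefore, the Week-12 disease evaluation should be performed in all non-PD patients". Footnote 12 of the schedule of assessments says the same and expressly includes patients who stopped treatment without progression. Protocol 6.3.3 ends all procedures for a patient who withdraws from the study altogether.

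**Other rules reaching the same patients.**
- Protocol 8.1, first paragraph, makes a patient evaluable after one complete cycle (or two doses over two cycles) with Week-6 and Week-12 assessments. Being on treatment at Week 12 is not required.
- Protocol 8.1, second paragraph, makes any patient who progresses before the Week-12 evaluation an evaluable non-responder.
- SAP 4 repeats both rules.
- Protocol 6.3.4, the section on replacement, does not list refusal.

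**The concern.** PFS3 is defined in Protocol 9.1 from the first administration and does not depend on agreeing to continue. A patient who declines further drug but stays on study can have a known primary outcome, and the refusal sentence removes that patient and recruits another whatever the outcome was.

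Two things are at stake. First, the plan does not determine who is counted. A refuser with both scans is evaluable under one sentence of 8.1 and replaced under another, and so is a refuser who progresses before Week 12. Two analysts could build different denominators for the futility decision and the final decision, and in an open-label trial that choice could be made with outcomes known. Second, if refusers differ in outcome from other patients, dropping them shifts the counted rate against a fixed 30% null.

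**Working it through.** **1. The plan's own figure.** Protocol 9.3 gives a null of 0.30, an alternative of 0.50, one-sided alpha 0.025, 90% power and the null variance for the test.

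n = [1.960·√(0.3·0.7) + 1.2816·√(0.5·0.5)]² / 0.20² = (0.898 + 0.641)² / 0.04 = 59.2, rounded up to 60.

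Critical count = 60·(0.30 + 1.960·√(0.21/60)) = 24.96, so 25. Approximate power is 0.904. The plan's 60 and 25 both reproduce.

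**2. Baseline with no selection.** For the exact two-stage rule, P(pass) = Σ over x = 7 to 24 of P(X₁ = x)·P(X₂ ≥ 25 − x), with X₁ ~ Bin(24, p) and X₂ ~ Bin(36, p). This gives 0.0355 at p = 0.30 and 0.918 at p = 0.50. That 0.0355 exceeds 0.025 comes from the rule itself and is a separate matter; 3.55% is the reference below.

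**3. Assumptions.** The documents give neither a refusal rate nor refusers' outcomes. Let f be the fraction of treated patients who refuse, q the fraction of refusers who are progression-free at Week 12, and 30% the true PFS3 in all treated patients.

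**4. Reading A: every refuser is discarded.** Counted rate = (0.30 − f·q)/(1 − f).

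| f | q | Counted rate | P(pass) |
|---|---|---|---|
| 5% | 0% | 31.6% | 0.063 |
| 5% | 15% | 30.8% | 0.048 |
| 10% | 0% | 33.3% | 0.108 |
| 10% | 15% | 31.7% | 0.065 |
| 5% or 10% | 30% | 30.0% | 0.0355 |
| 5% | 50% | 28.9% | 0.023 |
| 10% | 50% | 27.8% | 0.014 |

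**5. Reading B: the second paragraph of 8.1 governs.** Failing refusers stay in as non-responders and only progression-free refusers are dropped. Counted rate = (0.30 − f·q)/(1 − f·q). With f = 10%:
- q = 0%: 0.30/1 = 30.0%, P(pass) 0.0355.
- q = 15%: 0.285/0.985 = 28.9%, P(pass) 0.023.
- q = 30%: 0.27/0.97 = 27.8%, P(pass) 0.014.

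The counted rate cannot exceed 30% under this reading. Refusers who fail without recorded progression would put the result between A and B.

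**6. Effect on one result.** Suppose 25/60 (41.7%, exact 95% CI 29.1–55.1%) is reached after six refusers were replaced. With those six counted, the result is 25/66 (37.9%, CI 26.2–50.7%) if all failed and 31/66 (47.0%, CI 34.6–59.7%) if all were progression-free.

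**The case against.** The strongest reply is that the documents do not clearly discard failing refusers. The second paragraph of 8.1 covers any patient with progression, disease-related deterioration or death from malignant disease before the Week-12 evaluation, and the first paragraph covers a refuser with both scans. Read that way, the rule can only drop successes, which is conservative. This stands, and it is why the point is a conflict with an undetermined direction.

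It is also fair that the scan is called for but not guaranteed. The wording is that it should be done, and a patient who leaves the study has none. The point applies only to patients who stop treatment, stay on study and have a known status.

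Partial safeguards exist. SAP 6.2.2 plans an all-treated sensitivity analysis of PFS, with a 3-month estimate in Table 11.3.7, and Listing 10.1.4 shows non-evaluable patients with reasons. Neither touches the binomial 25/60 decision.

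A reader might infer that the plan inflates the false-positive rate to as much as 10.8%. The documents do not support that: it needs Reading A, an assumed refusal rate, and refusers who do much worse than the rest. A reader might also infer that only never-treated patients should be replaced. Nothing here bears on the other replacement grounds.

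**Conclusion.** The concern holds as a conflict between rules that leaves the primary denominator open and can drop a known primary outcome. Refusal alone is a replacement ground in Protocol 8.1, the synopsis and SAP 4. It is not one in Protocol 6.3.4, and it collides with the first two paragraphs of 8.1.

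Its size is conditional. With an assumed 5–10% refusal and a true PFS3 of 30%, the pass probability moves from 3.55% to 4.8–10.8% if all refusers are discarded and 0–15% of them are progression-free. It is 3.55% or less if failing refusers are retained, or if refusers do as well as or better than the others. That refusers do worse is plausible in this setting but undocumented. Reconciliation is worthwhile in either direction, because the choice should not be left until outcomes are known.

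**What to change.** - Remove refusal as a stand-alone replacement ground: the sentence in the synopsis, Protocol 8.1 and the evaluable-set definition in SAP 4, and the clause in the replacement paragraph of SAP 4.
- State that a refuser with known Week-12 status, or with earlier progression or death, is counted by that status.
- State that non-progression assessed after the start of new antitumor therapy is not a PFS3 success. Otherwise another drug's effect could be credited to PM060184.
- Add a PFS3 sensitivity analysis in all treated patients that counts those without a Week-12 assessment as PFS3 = No. SAP 11.3.1 does not already provide this, because its rule covers only patients who are already evaluable.
- Leave the other replacement grounds as they are, including the missing Week-12 assessment; a refuser who meets one of them is handled under it.

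The cost is a text change in four places and one extra table. N = 60 and the cut-offs 7/24 and 25/60 are unchanged, the scans are already scheduled, and fewer replacements may be needed. The downside is that the reported PFS3 rate may be slightly lower.
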